#### **7.1.1. Temporary Discontinuation/Study Intervention Interruption**

The decision to interrupt study intervention administration will be at the discretion of the investigator, with input from the medical monitor.

## **7.2. Participant Discontinuation/Withdrawal From the Study**

- A participant may withdraw from the study at any time at their own request for any reason (or without providing a reason).
- A participant may be withdrawn at any time at the discretion of the investigator for safety, behavioral, or compliance reasons.
- The participant will be permanently discontinued both from the study intervention and from the study at that time.
- If the participant withdraws consent for disclosure of future information, the sponsor may retain and continue to use any data collected before the withdrawal of consent.
- If a participant withdraws from the study, they may request destruction of any samples taken and not tested, and the investigator must document this in the site study records.

## **7.3. Lost to Follow-up**

A participant will be considered lost to follow-up if they repeatedly fail to attend scheduled visits and is unable to be contacted by the study site.

The following actions must be taken if a participant fails to attend a required study visit:

- The site must attempt to contact the participant, reschedule the missed visit as soon as possible, counsel the participant on the importance of maintaining the assigned visit schedule, and ascertain whether the participant wishes to and/or should continue in the study.
- Before a participant is deemed lost to follow-up, the investigator or designee must make every effort to regain contact with the participant (where possible, 3 telephone calls and, if necessary, a certified letter to the participant's last known mailing address or local equivalent methods). These contact attempts should be documented in the participant's medical record.
- If the participant continues to be unreachable, they will be considered to have withdrawn from the study and be lost to follow-up.

## **8. STUDY ASSESSMENTS AND PROCEDURES**

- Study procedures and their timing are summarized in the SoA (Section 1.3).
- Adherence to the study design requirements, including those specified in the SoA, is essential and required for study conduct.
- Decentralized participants will undergo consent, initial screening, and data collection procedures via online tools using an electronic device (computer or smart phone) with an active internet connection. Completion of some screening assessments will also require in-person presence of study personnel at the participant's location as specified in the SoA (Section 1.3). When the study intervention is prescribed, the principal investigator or a subinvestigator will be present via telemedicine, and study personnel may be present at the participant's location.
- Some assessments will occur as telemedicine visits as specified in the SoA (Section 1.3).
- All screening evaluations must be completed and reviewed to confirm that potential participants meet all eligibility criteria. The investigator should maintain a screening log to record details of all participants screened and to confirm eligibility or record reasons for screening failure, as applicable.
- Procedures conducted as part of the participant's routine clinical management and obtained before signing of the ICF may be utilized for screening or baseline purposes, provided that the procedures met the protocol-specified criteria and were performed within the time frame defined in the SoA.
- Instructions will be provided to participants at each visit on relevant aspects of the study.
- Unscheduled visits may be needed (eg, for repeating the 24-hour BP recording assessment [if needed], returning the BP recording device, or any other reason at the investigator's discretion).
- In the event of a significant study-continuity issue (eg, caused by a pandemic), alternate strategies for participant visits, assessments, medication distribution, and monitoring may be implemented by the sponsor or the investigator, per local health authority/ethics requirements.

### **8.1. General Administrative Procedures**

#### **8.1.1. Informed Consent**

The investigator or medically qualified designee (consistent with local requirements) must obtain documented consent from each potential participant/legal representative prior to participation in this study. A signed copy of the ICF should be given to the participant, and the original should be placed in the participant's medical records.

This hybrid study will allow participants to enroll either virtually or at a site. Local guidelines and regulations will be followed when using eConsent.

### **8.1.2. Assignment of Participant Number**

Each participant who signs the ICF will be assigned a unique number that will identify the participant throughout the study. Once a number has been assigned, it cannot be reassigned to another study participant.

### **8.1.3. Medical History**

A medical history will be obtained by the investigator or a medically qualified designee (consistent with local regulations). All active conditions and any condition diagnosed within the participant's lifetime that the investigator deems clinically significant should be recorded.

### **8.1.4. Medication Review (Prior and Concomitant Medications)**

The investigator or medically qualified designee should review the participant's prior medication use. All medication taken by the participant (ie, prior medications within approximately 2 months before screening and concomitant medications during the study) should be recorded.

### **8.1.5. Inclusion and Exclusion Criteria Review**

All inclusion and exclusion criteria should be reviewed by the investigator to ensure that the participant qualifies for the study.

### **8.1.6. Timing of Study Intervention Dosing**

XYWAV should be administered at least 2 hours after eating.

Participants should take each dose of XYWAV while in bed, lie down immediately after dosing, and remain in bed following ingestion of each dose. With twice-nightly dosing, participants may need to set an alarm to awaken for the second dose. If the second dose is missed, that dose should be skipped and XYWAV should not be taken again until the next night. Two XYWAV doses should never be taken at 1 time.

Dosing and dose adjustments are discussed in Section 4.3 and Section 6.6, respectively.

## **8.2. Efficacy Assessments**

Planned time points for all efficacy assessments are provided in the SoA (Section 1.3).

### **8.2.1. 24-Hour Blood Pressure Monitoring**

Ambulatory BP monitoring is a standard technique in adult antihypertensive studies to assess the magnitude and duration of effect of investigational drugs.

Participants will receive training on the use of the ambulatory BP monitors and will be provided a device for 24-hour home recording of BP.

During the Screening Period, the 24-hour BP recording should not be initiated until all other eligibility criteria have been assessed and are met (however, the BP recording can be initiated prior to obtaining results from the clinical laboratory assessments at screening). This recording at screening must occur no more than 2 weeks prior to the switch from twice-nightly high-sodium oxybate to XYWAV.

The same device should be used to collect each 24-hour BP recording on the participant during the study. Additionally, participants are required to wear the device for approximately 25 hours for each recording to ensure that 24 hours of data are captured.

Participants will be asked to make every effort to capture each 24-hour BP recording beginning at the same start time and on days matched based on activity level. For example, if a participant works from home and exercises on Monday and Wednesday and works out of the office and does not exercise on Tuesday and Thursday, these 2 groups of “routine days” should be matched. In this example, a 24-hour BP recording starting on Monday during the Screening Period should be matched to a 24-hour recording starting on either Monday or Wednesday during the EOT Visit.

The ambulatory BP device will obtain BPs every 20 minutes during the daytime and every 30 minutes during the nighttime over the 24-hour time frame. Once each 24-hour recording is captured, the BP data will be reviewed to confirm adequate collection according to quality control criteria (ie, obtain  $\geq 80\%$  of the programmed recordings [a minimum of 50 ambulatory BP measurements] and have  $\leq 2$  hours contiguous loss of BP readings).

Study personnel (either at the investigational site or at the participant’s location) will place the ambulatory BP device on the participant and initiate the 24-hour BP recording. The device can be removed by the participant after completion of the 24-hour BP recording, with detailed instructions from study personnel.

The participant will return to the site with the ambulatory BP device (site-based participants) or study personnel will go to the participant’s location (decentralized participants) within 3 days after the conclusion of the 24-hour BP recording (as specified in the SoA [Section 1.3]). At this time, the 24-hour BP data will be assessed for quality criteria. If the 24-hour BP data does not meet the quality criteria, the ambulatory BP device will be placed on the participant to obtain another 24-hour BP recording. Up to 2 additional 24-hour BP recordings may be attempted within 3 days after the prior collection.

### **8.2.2. 24-Hour Urine Collection**

Participants will receive supplies and instructions on the 24-hour urine collection at the time points specified in the SoA (Section 1.3). This collection should occur within 72 hours of the 24-hour BP recording, but this can be extended to 1 week if necessary. The 24-hour urine collection during the Screening Period must occur (but results do not need to be available) prior to the switch from twice-nightly high-sodium oxybate to XYWAV. The total amount of urine sodium excreted over the 24-hour period will be determined based on the sodium concentration and total volume of urine collected over 24 hours.

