24-Hour urine collection	X						X	X		Should occur within 72 hours of the 24-hour BP recording (can be extended to 1 week if necessary). Must occur (but results do not need to be available) before the switch to XYWAV.
24-Hour BP monitoring a	X						X	X		
 
Screening recording should occur after all eligibility criteria are met (but laboratory results do not need to be available) and ≤ 2 weeks prior to the switch to XYWAV.
 
Participants must return device within 3 days after the conclusion of the recording (which will require an additional site visit).
 
Refer to Section 8.2.1.
 

Participant instructions	X	X	X	X	X	X	X	X	X	
Sleep diary	X					X	X	X		
 
To be completed daily for approx 7 days around the time of (and including) each 24-hour BP recording.
 
To be completed concurrently with the study intervention dosing diary.
 
Site personnel should initialize diary at each specified visit and review diary data entries during each approx 7-day period.
 
Refer to Section 8.2.3.
 

Procedure	Screening Period (twice-nightly high-sodium oxybate)	Intervention Period (XYWAV) Telemedicine Visits shaded in gray						E/D	Safety Follow-up Visit	Notes
		Switch to XYWAV					End of Treatment Visit			
Study Visits	V1 a	V2	V3	V4	V5	V6	V7 a		V8	Additional unscheduled visits will be needed a .
Scheduled Day(s)	-14	1	7	14	28	35	42*		56**	*Study intervention to be taken each night until the EOT 24-hour BP assessment has met minimum data quality standards a . **SFU Visit should occur 14 days (+ 3 days) after the last dose of study intervention or E/D Visit (as applicable).
Study Visit Window (days)	-7 (ie, Day -21)		± 3	± 3	± 3	± 3	± 3		+ 3	
Study intervention dosing diary	X					X	X	X		
 
Before the switch to XYWAV (ie, at screening), diary will capture the use of twice-nightly high-sodium oxybate.
 
To be completed daily for approx 7 days around the time of (and including) each 24-hour BP recording.
 
To be completed concurrently with the sleep diary.
 
Site personnel should initialize diary at each specified visit and review diary data entries during each approx 7-day period.
 
Refer to Section 6.5 and Section 8.2.3.
 

C-SSRS	X									Administered by qualified site rater.
PGIs	X						X	X		
PGIc							X	X		

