### 2.2. Background

Narcolepsy is a life-long neurologic disease for which no cure has been identified. The worldwide prevalence of narcolepsy is estimated to be 0.02% to 0.067% ([Ohayon, 2007](#)), and in the US, the disease afflicts approximately 1 in 2000 individuals ([Majid, 2010](#)). Narcolepsy has been defined as a REM sleep disorder resulting from dysregulation of the sleep-wake cycle ([Nishino, 2007](#)). It is characterized by pathological sleepiness, commonly termed excessive daytime sleepiness or EDS, and includes disrupted nighttime sleep and abnormal REM sleep manifestations, including cataplexy, sleep paralysis, and hypnagogic or hypnopompic hallucinations ([Boscolo-Berto, 2012](#); [Dauvilliers, 2012](#)).

XYREM (sodium oxybate) has been available in the US since 2002 and is indicated in the US for the treatment of cataplexy or EDS in patients 7 years of age and older with narcolepsy ([XYREM USPI](#)). XYREM is also approved in Canada for the treatment of cataplexy in patients with narcolepsy ([XYREM Canadian Product Monograph](#)) and in the EU ([XYREM EU SmPC](#)) for the treatment of narcolepsy with cataplexy in adult patients, adolescents, and children from the age of 7 years.

While XYREM has been shown to have a positive risk-benefit profile when prescribed per recommended label and has been designated as standard of care for the treatment of cataplexy and EDS by the American Academy of Sleep Medicine ([Morgenthaler, 2007](#)), the current formulation of XYREM imparts a significant amount of additional sodium to an individual's daily dietary salt intake. The AHA and FDA have recommended an intake of no more than 2300 mg of sodium per day, with an ideal limit of no more than 1500 mg per day for most adults ([FDA, 2016](#); [AHA, 2018](#)).

An increased risk of cardiovascular disease has been causally associated with high sodium intake ([Whelton, 2012](#); [FDA, 2016](#); [NASEM, 2019a](#); [Zeng, 2022](#)). Administration of the maximum

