  - Participants will continue taking study intervention until the EOT 24-hour BP recording meets minimum data quality standards (quality control criteria are defined in Section 8.2.1). If needed, participants may repeat the EOT 24-hour BP recording up to 2 additional times, which would increase the duration of the Intervention Period and, consequently, the overall duration of study participation.
  - After completing an EOT 24-hour BP recording that meets minimum data quality standards, participants may transition to commercial XYWAV (as permitted by local health authorities) or other standard of care per physician discretion.

- A Safety Follow-up Visit (to be scheduled at least 14 days after the last dose of study intervention).

This will be a hybrid study to allow participants to enroll either virtually (decentralized participants) or at an investigational site (site-based participants).

Decentralized participants are participants who are enrolled virtually and who will not have any assessments performed physically at an investigational site. However, some assessments will require in-person presence of study personnel at the participant's location.

Site-based participants are participants who are enrolled at an investigational site and will have some assessments performed at that site. Note that participants in the EU will only enroll in this study as site-based participants. All site-based participants will still attend 3 decentralized (ie, telemedicine) study visits per the SoA (Table 3). Site-based participants will always have the option to be seen in person at the clinic for these 3 decentralized visits, if needed.

Additionally, all participants in this study will use electronic clinical outcome assessment devices at home. Diary and assessment information will be collected via a smartphone, which will be managed by the participant at home. In addition, BP data will be collected over a 25-hour period using a 24-hour ambulatory BP monitoring device. The BP device will be placed on the participant's arm and initialized in-person by trained site staff and will continue to be worn by participants at home (Section 8.2.1). Site staff will train participants in person on the use of these devices and how to report any AEs (serious and nonserious) that may occur during the study. Participants will also be provided with site and vendor 24-hour contact details for support with any safety or device issues that may arise.

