## **6.7. Continued Access to Study Intervention After the End of the Study**

At the end of the Intervention Period (after completing an EOT 24-hour BP recording that meets minimum data quality standards [Section 4.1]), participants may transition to commercial XYWAV (in countries where XYWAV has been approved) or another standard of care per physician discretion.

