### 7.3.3. 24-Hour Urine Sodium Excretion

24-hour urine sodium excretion at each visit, including change from baseline, will be summarized as continuous variables.

At baseline and EOT, correlation between 24-hour average SBP and 24-hour urine sodium excretion at each visit will be assessed visually by scatterplots and analytically by Pearson and Spearman coefficients.

At EOT, correlation between 24-hour average SBP change from baseline and 24-hour urine sodium excretion change from baseline will be assessed visually by scatterplots and analytically by Pearson and Spearman coefficients.

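### The EOT 24-hour urine may be collected after a participant is released from study XYWAV, so the exploratory sodium analyses can include samples taken on another treatment

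*Protocol*

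**What the plan says.** Protocol Section 8.2.2 sets one timing rule for both urine collections: "This collection should occur within 72 hours of the 24-hour BP recording, but this can be extended to 1 week if necessary". It does not say whether the collection comes before or after the recording. It then adds a treatment condition for one of the two: "The 24-hour urine collection during the Screening Period must occur (but results do not need to be available) prior to the switch". Table 3 repeats this ("Must occur (but results do not need to be available) before the switch to XYWAV"), and Table 4 has the same rule for decentralized participants. Neither the section nor the tables set a matching condition for the EOT sample.

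Release from study drug is governed elsewhere. Tables 3 and 4 keep participants on XYWAV until the EOT BP recording meets the quality standard. Section 4.1 continues: "After completing an EOT 24-hour BP recording that meets minimum data quality standards, participants may transition to commercial XYWAV", subject to local permission, "or other standard of care per physician discretion". Section 6.7 has the same trigger and limits commercial supply: "in countries where XYWAV has been approved) or another standard of care per physician discretion". The urine collection is not mentioned as a condition in any of these places.

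SAP Section 7.3.3 summarises urine sodium and its change from baseline, and at EOT examines the "correlation between 24-hour average SBP change from baseline and 24-hour urine sodium excretion change from baseline". SAP Section 5.2.3 assigns data to visits by the CRF visit at which they were collected, unless otherwise specified.

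**The concern.** The protocol recognises at screening that a urine sample is informative only if it reflects the oxybate the participant is meant to be taking. At EOT that protection is missing. A sample collected late, after a valid BP recording and after a change of treatment, would pair BP measured on XYWAV with sodium excreted on something else, and nothing visible in either document would mark it as different.

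At stake is the exploratory evidence on mechanism. The trial has no control group, and its hypothesis is that the BP fall follows from a lower sodium load. Serum sodium is in the clinical chemistry panel, but clinical labs are scheduled only at screening. The 24-hour urine is therefore the only laboratory measure of sodium after the switch.

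**Working it through.** **1. The plan's own sodium figure.** Protocol Section 2.2 gives, at 6 to 9 g/night, 1100 to 1638 mg sodium for XYREM and 87 to 131 mg for XYWAV.

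- 1100 − 87 = 1013 mg/day
- 1638 − 131 = 1507 mg/day

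This reproduces the stated reduction. At 22.99 mg per mmol it is 44.1 to 65.6 mmol/day.

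**2. Days exposed.** Let L be the last permitted day for urine after the recording (3 by default, 7 if extended; Section 8.2.2). Let q be the day on which the recording passes its quality check. Section 8.2.1 has the device returned, or staff attending, within 3 days of the end of the recording, and quality is assessed then, so q runs from 0 to 3. Dosing continues until the check passes, so the exposed days are L − q (counting both from the end of the recording).

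| Quality check passes on day q | 72-hour window (3 − q) | 1-week extension (7 − q) |
|---|---|---|
| 0 | 3 | 7 |
| 1 | 2 | 6 |
| 2 | 1 | 5 |
| 3 | 0 | 4 |

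The exposure lies mainly in the extension. Collection before or during the recording is also permitted and carries no such exposure.

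**3. What the participant may be taking then.** Commercial XYWAV leaves the sodium load unchanged, so those samples remain valid. The alternative is other standard of care. The protocol does not name it, but Section 2.2 says that XYREM "has been designated as standard of care for the treatment of cataplexy and EDS", and every participant entered the study on high-sodium oxybate. A return to it is thus allowed by the text.

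**4. Effect on the sodium analyses.** For a participant back on the prior dose, the oxybate-related change at urine collection could be as little as 0 instead of −1013 to −1507 mg/day. This is an upper bound, because it assumes that excretion has fully re-equilibrated. If a share f of the analysed participants is in that position:

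- expected mean change = −(1 − f) × (1013 to 1507) mg/day
- loss of contrast = f × (1013 to 1507) mg/day

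The documents give no value for f. By way of illustration only, f = 5% loses 51 to 75 mg/day, 10% loses 101 to 151, 20% loses 203 to 301 and 30% loses 304 to 452.

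The correlation is affected too, since those participants' sodium change no longer belongs to the treatment under which their BP change was measured. The size of that effect cannot be derived, because the documents give no SD for urine sodium.

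**5. Whether the SAP would catch it.** A late sample filed under the EOT visit is taken as EOT under SAP Section 5.2.3, and Section 7.3.3 has no on-treatment condition.

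**The case against.** The strongest reply is that on-treatment collection is already intended. Section 4.1 places the repeat BP recording and urine collection at the EOT Visit, after about 6 weeks of XYWAV, and counts that visit as part of the Intervention Period. Tables 3 and 4 put the urine at Visit 7 under the XYWAV heading and dispense XYWAV again at that visit. Section 6.7 speaks of transition at the end of the Intervention Period. This stands as evidence of intent: a reader might infer that the plan means to sample off drug, and it does not. But the same sections make the BP recording alone the trigger for release, and the 1-week extension applies at EOT as well. The fault is unclear drafting that leaves a mismatch within the rules.

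Second, harm needs several things to coincide: urine collected after the recording, the quality check already passed, a transition already made, and made to high-sodium oxybate rather than to commercial XYWAV. This also stands. It is why no overall bias can be stated, and why it would be wrong to treat the whole week after the recording as exposed.

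Third, affected samples might be identified from the dosing diary around the recording, the study drug stop date and the concomitant medication dates. That is correct and makes the repair cheap, but neither document uses these data to judge the urine sample. The post-study narcolepsy treatment item covers US participants only.

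Finally, part of the exploratory text is redacted, so a general condition there cannot be ruled out. Section 7.3.3 itself is visible and contains none.

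**Conclusion.** The point holds as a correctable mismatch between the urine window and the release rule. A urine collected after release from study XYWAV is within protocol, may reflect high-sodium oxybate, and would be analysed as EOT. The exposure is 4 to 7 days of the 1-week window and 0 to 3 days of the 72-hour window. The loss per affected participant is at most the full 1013 to 1507 mg/day. That bound assumes a return to the prior dose and full re-equilibration by the time of collection.

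Four stronger readings are not supported:

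- That urine sodium will measure the wrong treatment. Off-XYWAV collection is permitted, not required, and high-sodium oxybate as the next treatment is a fair inference, not a stated plan.
- That the mean sodium fall is biased by a known amount. The share affected is not in the documents.
- That the problem clusters where commercial XYWAV is unavailable. This is plausible, but the documents give no enrolment by country.
- That the main result is at risk. The primary and secondary BP endpoints do not use the urine, and the urine sodium analyses lie outside the testing hierarchy.

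The change is worth making because it is cheap and protects the only post-switch laboratory sodium measure.

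**What to change.** **Protocol.** Reconcile Section 8.2.2 and the urine rows of Tables 3 and 4 with Sections 4.1 and 6.7 by mirroring the screening rule. The EOT 24-hour urine would be scheduled before or concurrent with the EOT BP recording, and completed before any transition to a non-XYWAV oxybate. This concerns the timing of an assessment only; it changes no dose or treatment rule.

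**SAP Section 7.3.3.** Include an EOT urine value in the change and correlation analyses only if collection was completed before the first dose of any non-XYWAV oxybate. Keep samples taken on study or commercial XYWAV: a cut-off at the last dose of study drug would discard valid samples from participants who moved to the commercial product. List the excluded values. Flag early-discontinuation samples taken off XYWAV in the same way, since that visit follows discontinuation.

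**Cost.** One sentence in the protocol and schedules, and one inclusion condition in the SAP. It would use the diary, dosing and concomitant medication dates that the protocol already has recorded, set against the urine collection date. The price is slightly less scheduling flexibility and a few excluded late samples.
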